7.1 Dose Escalation

The selection of the starting dose of 200 mg QD is based on in vivo data from nonclinical pharmacological models, toxicologic results, and estimated PK parameters for humans.

In accordance with guidelines for starting dose selection for investigational agents in cancer patients, dose ratios were calculated using the severely toxic dose in 10% (STD10) in rats and non-rodent highest non-severely toxic dose (HNSTD). The rat 28-day repeated-dose toxicology study did not establish a lethal dose in 50% of animals (LD₅₀) or a STD10. However for the purposes of calculating a clinical starting dose for oncology, Plexxikon has assumed the highest dose tested in the rat study (200 mg/kg) to be the STD10. The dog study also did not establish a LD₅₀, and thus the 300 mg/kg dose was considered to be the HNSTD. Using this algorithm and estimating the rat 1/10 x STD10 to be 20 mg/kg, a maximum recommended starting dose (MRSDD) of 200 mg (or ~120 mg/m²) is proposed. Based on a comparison the 1/10 x STD10

(after converting mg/kg dose to mg/m²) to either the efficacious dose in the mouse BaF3 model or the proposed human MRSD of 200 mg, dose ratios for the rat (vs. human) were 13 and 1, respectively. The dose ratios in the dog, based on these assumptions and estimating the dog 1/6 x HNSTD to be 50 mg/kg, were 111 and 8.

Safety margins were also calculated by comparing values for free drug exposure (AUC) in rats and dogs at their 1/10 STD or 1/6 HNSTD, respectively. Pexidartinib is strongly protein bound in plasma of dogs, rats, and humans thus the fraction of pexidartinib unbound is a more meaningful comparison. In the comparison of rat vs. human, this method yielded an exposure ratio of 72, based on the predicted AUC of 14 ng•hr/mL at the proposed MRSD of 200 mg. Applying the same method of comparison and assumptions, exposure ratios of 2.4 and 10 were obtained for dog vs. human.

In the case of calculating safety margins based on free drug exposure, the safety margin based upon the maximum recommended starting dose in humans is 10 or above. Thus, based on either dose ratios or free drug exposure ratios, the proposed MRSD of 200 mg in humans should represent a minimally effective dose with only a limited safety risk.

For dose escalation planning, the effects of pexidartinib on bone marrow appear to be the most predictive of Fms and Kit activity on normal tissue. In both rats and dogs, both the incidence and severity of bone marrow hypocellularity with resulting decreased peripheral WBC counts is approximately linear with increasing dose and systemic exposure. This supports the planned dose escalation design as proposed in [Section 16.4](#).

7.2 Route and Regimen

Oral dosing with pexidartinib is planned for this study. Adequate systemic exposure is expected by oral administration. The proposed regimen for the first cohort is once daily. A twice-daily dosing regimen may be instituted for subsequent cohorts after review of the PK data from the initial cohort. For the Extension cohorts, the dose regimen is BID.

7.3 Treatment Period

The proposed treatment period of 28 days (initial phase) was initially supported by 28 days of GLP general toxicology studies in 2 species for the 200 mg starting dose. Pexidartinib will be offered to each patient as long as both the patient and investigator agree that it continues to be well tolerated, and there has been no evidence of clinical disease progression.

8.0 OBJECTIVES

8.1 Primary

The primary objective for the dose escalation phase of this study is to evaluate the safety and PK of pexidartinib in patients with solid tumors. The primary objective of the Extension cohorts is to evaluate the potential of pexidartinib as a single agent to provide clinical benefit in patients with

specific malignancies, based on literature, pharmacology data, or responses in the dose escalation phase of the study.

8.2 Secondary

The secondary objective is to measure the pharmacodynamic activity of pexidartinib via plasma and urine biomarkers of Fms activity (all cohorts).

9.0 DESIGN

9.1 Description

Dose Escalation Cohorts:

This is an open-label, ascending dose trial of daily oral doses of pexidartinib administered to patients with solid tumors at approximately 4 investigational sites. A cohort of 3 patients will be assigned to the first dose group to receive 200 mg QD of pexidartinib. PK samples will be obtained after the first dose (through 8 hours) on C1D1 and prior to the first dose on C1D2. Patients will return to the clinical site on C1D8 for assessment of adverse events, PK (predose), and clinical laboratory assessments. They will then return to the clinic on C1D15 for evaluation of safety (AEs, clinical laboratory assessments, vital signs, ECG) and PK. Each cycle is defined as 28 days. If adequate safety and tolerability have been demonstrated for one cycle of 28 days at this dose level, the next cohort of 3 patients will be enrolled and treated with pexidartinib once or twice daily in a similar fashion as the first cohort. Each cohort will return to the clinic after 4 weeks of dosing for a repeat evaluation of safety. Three patients will be enrolled to each dose level in the absence of Grade 2 or greater drug-attributable toxicity. Dose escalations of 100% are planned until the occurrence of drug-attributable Grade 2 or greater toxicity. In the absence of DLT, dose escalation will proceed sequentially by 50% increments from that point forward.

In selected cohorts, 3–6 patients will be treated with a pexidartinib dose of either 100 mg QD or 200 mg QD during a one-week run-in period before increasing to the full dose for that cohort, in order to profile the pharmacodynamic (PD) dose response activity of pexidartinib at doses below 300 mg QD.

Assignment of patient study numbers and verification of dose selection will be coordinated by the CRO assigned by the Sponsor, in collaboration with the Sponsor. A teleconference attended by the participating investigators, the CRO personnel, and the Sponsor will be held weekly or as needed to assess cumulative safety data and jointly confirm a decision to expand a cohort or dose escalate, in accordance with the criteria set forth in [Section 16.4](#).

After the initial 4 weeks of dosing, all patients will be able to continue receiving pexidartinib at their assigned dose provided they meet the criteria described in [Section 13.8](#). Patients will return for clinical evaluation every 28 days and will have radiographic assessments (solid tumors) for response and progression after every two months of drug administration.

Extension Cohorts:

At the recommended Phase 2 dose of 1000 mg/day, a total of six Extension cohorts will be enrolled and followed for safety and tumor response as assessed by CT scan every 8 weeks (or, beyond Cycle 40, every 24 weeks). Participants will remain on treatment until tumor progression, as long as there are no unacceptable toxicities.

9.2 Number of Patients

Up to 50 patients will participate in the study in the dose escalation phase of the study. Approximately 10 patients will be enrolled in each of the five disease-specific Extension cohorts and up to 20 patients can be enrolled in the miscellaneous Extension cohort, for a total of approximately 70 patients with the possibility of 30 additional patients in a specific cohort if necessary ([Section 24.6](#)).

9.3 Number of Study Centers

For dose escalation, the study will be performed at approximately 4 investigational sites. For the extension cohorts, up to approximately 18 sites will participate.

9.4 Duration of Patient Participation

Each patient in the dose escalation phase of the study will participate in the study for 4 weeks at the designated dose, and then will be offered continued dosing with pexidartinib if it is well tolerated and in the absence of tumor progression. Patients in the Extension cohorts will be offered continued dosing with pexidartinib if it is well tolerated and in the absence of tumor progression.

9.5 Duration of Study

The duration of the study is contingent on the number of dose levels in the dose escalation phase. Each dose escalation cohort will take approximately 6 weeks (7 weeks for cohorts that include a one-week run-in period), including 2 weeks of recruitment. For the Extension cohorts, patients will be treated with study drug until progression or toxicity, until the phase 4 PVNS continuation study has been opened. Upon study termination, patients that don't transition to the phase 4 continuation study will be provided information regarding potential transition to commercial drug.

10.0 SELECTION OF STUDY POPULATION

All patients must participate in the consent process. During the consent process, the person obtaining consent must inform the patient of all elements of informed consent. No protocol-specific procedures, including screening procedures, are to be performed until the patient has signed and dated an institutional review board (IRB)/independent ethics committee (IEC)-

approved informed consent form. The study begins with the signing and dating of the informed consent form. Patients must also meet the inclusion and exclusion criteria to be enrolled in the study.

10.1 Inclusion Criteria

1. Male or female patients ≥ 18 years old
2. For the dose escalation cohorts, patients with advanced, incurable, solid malignancies in which the target kinases are thought to be linked to disease pathophysiology and whose cancers are confirmed histologically. The tumors must fulfill BOTH of the following criteria: a) refractory to standard therapy, OR standard or curative therapy does not exist or is not considered appropriate by the investigator, AND b) tumor proliferation or metastasis could be driven or promoted in part by Flt3, Kit, or Fms/CSF-1 activity.
3. For the Extension cohorts, patients must have measurable disease by RECIST v1.1 criteria and meet the following disease-specific criteria:
 - a. For advanced or recurrent MEC of the salivary gland, patients must not be candidates for curative surgery or radiotherapy.
 - b. For PVNS (including tenosynovial giant cell tumor), patients must have a histologically confirmed diagnosis of inoperable progressive or relapsing PVNS, or resectable tumor requiring mutilating surgery, as well as demonstrated progressive disease in the last 12 months.
 - c. For GIST, patients must have failed previous therapy with imatinib and sunitinib. Patients with known PDGFR mutations are excluded, but mutation testing is not required for study entry.
 - d. For ATC, patients must have histologically or cytologically diagnosed advanced ATC.
 - e. For metastatic solid tumors with documented malignant pleural, pericardial, and/or peritoneal effusions, patients must not be receiving specific therapy for the effusion (other than periodic drainage by needle) or have an indwelling drain.
 - f. Other solid tumor types can be included in a miscellaneous cohort, provided there is a clear scientific rationale for treatment with pexidartinib and upon approval by the Medical Monitor.
4. Women of child-bearing potential must have a negative pregnancy test within 7 days of initiation of dosing and must agree to use an acceptable non-hormonal method of birth control from the time of the negative pregnancy test up to one month after the last dose of study drug, Women of non-childbearing potential may be included if they are either surgically sterile or have been postmenopausal for ≥ 1 year. Fertile men must also agree to use an acceptable method of birth control while on study drug and for one month after the last dose of study drug.
5. All associated toxicity from previous or concurrent cancer therapy must be resolved (to \leq Grade 1 or Baseline) prior to administration of pexidartinib.

6. Willing and able to provide written informed consent prior to any study related procedures and to comply with all study requirements.
7. ECOG performance status 0 or 1.
8. Life expectancy ≥ 3 months.
9. Adequate hematologic, hepatic, and renal function (absolute neutrophil count $\geq 1.5 \times 10^9/L$, Hgb >9 g/dL, platelet count $\geq 100 \times 10^9/L$, AST/ALT $\leq 2.5 \times$ ULN or $<5 \times$ ULN in the presence of liver metastases, albumin ≥ 3 g/dL, creatinine $\leq 1.5 \times$ ULN or calculated CrCl >60 mL/min using Cockcroft-Gault formula).

10.2 Exclusion Criteria

1. Specific anti-cancer therapy within 3 weeks prior to study drug administration.
2. Investigational drug use within 28 days of the first dose of pexidartinib.
3. Uncontrolled intercurrent illness.
4. Refractory nausea and vomiting, malabsorption, external biliary shunt, or significant small bowel resection that would preclude adequate absorption.
5. QTcF ≥ 450 msec (for males) or ≥ 470 msec (for females) at screening.
6. The presence of a medical or psychiatric condition that, in the opinion of the Principal Investigator, makes the patient inappropriate for inclusion in this study.

10.3 Screen Failures

Patients who sign an informed consent form, are not assigned to a treatment, and do not receive test article are defined as screen failures. For all screen failures, the investigator is to maintain a screening log that documents the screening number, patient initials, and reason(s) for screen failure. A copy of this log should be retained in the investigator's study files.

11.0 PRIOR TREATMENT

Reasonable efforts will be made to determine all relevant treatment received by the patient within 1 month before administration of the test article and within 14 days before test article administration for over-the-counter drugs. All previous treatments for the solid tumor should be recorded. Relevant information must be recorded on the patient's case report form (CRF). This should include the name of the procedure or drug and other information required on the CRF.

12.0 CONCOMITANT TREATMENT

Concomitant treatment is permitted if the medication is not expected to interfere with the evaluation of safety or efficacy of the study drug. During the study, if the use of any concomitant treatment becomes necessary (e.g., for treatment of an adverse event), the treatment must be

recorded on the CRF, including the reason for treatment, generic name of the drug, dosage, route, and date and time of administration.

12.1 CYP3A and UGT Inhibitors

Although pexidartinib does not appear to inhibit CYP drug-metabolizing enzymes to an important extent, caution is warranted when administering pexidartinib to subjects taking drugs that are highly dependent on CYP3A4 for metabolism and have a narrow therapeutic index. It is not known whether systemic exposure to these medications will demonstrate an increase while patients are receiving pexidartinib.

Of the five major CYP isoforms, 3A4 (BFC) may be involved in Phase I metabolism of pexidartinib, with possibly CYP1A2 playing a minor role (see [Attachment 5](#) for a list of common CYP3A4 inhibitors and inducers). In general, strong inducers of CYP3A4 should be avoided unless clinically necessary. These include anticonvulsants, mycin antimicrobials, and antiretrovirals. Some common examples include inducers such as rifampicin, carbamazepine, phenytoin, efavirenz, and nevirapine.

Avoid concomitant use of pexidartinib with moderate or strong CYP3A inhibitors or uridine diphosphate glucuronosyltransferase (UGT) inhibitors. If concomitant use with a moderate or strong CYP3A inhibitor or UGT inhibitor cannot be avoided, reduce the pexidartinib dose according to the recommendations in [Table 2](#). If concomitant use of a moderate or strong CYP3A inhibitor or UGT inhibitor is discontinued, increase the pexidartinib dose (after 3 plasma half-lives of the moderate or strong CYP3A inhibitor or UGT inhibitor) to the dose that was used before starting the inhibitor.

Table 2: Recommended Dosage Reductions for Pexidartinib with Concomitant Use of Moderate or Strong CYP3A Inhibitors or UGT Inhibitors

Current Total Daily Dose	Modified Total Daily Dose	Administration of Modified Total Daily Dose
800 mg	400 mg	200 mg twice daily
600 mg	400 mg	200 mg twice daily
400 mg	200 mg	200 mg once daily

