A series of in vitro studies examined the metabolic stability of pexidartinib using either liver S9 fraction or intact hepatocytes from several species, including rats and dogs, the two species used in toxicology studies, as well as humans. Studies with intact hepatocytes revealed that pexidartinib was very slowly metabolized in all three species, especially human liver cells. Although the exact molecular species were not identified, in the presence of human hepatocytes, several molecular species corresponding to glucuronide conjugates were detected, with minimal evidence of breakdown. These data, along with the high protein binding, suggests that the clearance of pexidartinib from human plasma may be slow. Another study was conducted to

evaluate the CYP450 phenotypes of pexidartinib metabolism in vitro. Of the five major CYP isoforms, 3A4 (BFC) may be involved in Phase I metabolism of pexidartinib, with possibly CYP1A2 playing a minor role.

Pexidartinib does not appear to inhibit CYP drug-metabolizing enzymes to an important extent. Studies using human liver microsomes yielded enzyme inhibitory constant (K_i) values exceeding 30 μM for CYP1A2 and 3A4 (testosterone substrate), ≥ 12 μM for 3A4 (midazolam substrate), 2D6 and 2C9. A K_i value < 10 μM was obtained for only one CYP isozyme: 2C19 ($K_i = 8.4$ μM). It is worth noting that the latter experiment was conducted in the absence of HSA. When pexidartinib was evaluated for its ability to inhibit the major human CYP isozymes in the presence of 10 μM human serum albumin (HSA), IC_{50} values greater than 30 μM were uniformly obtained.

In another series of experiments, pexidartinib was demonstrated not to induce the expression of genes that encode CYP enzymes and several other proteins involved in metabolism and transport.

In aggregate, an extensive series of non-clinical studies evaluating pexidartinib reveal a metabolically stable drug that displays extensive protein binding. Clinically relevant drug-drug interactions are not anticipated based upon experimental evidence of negligible CYP inhibition or induction in vitro.

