12.2 Hormonal Contraceptives

Pexidartinib has been indicated to be a moderate CYP3A4 inducer, as concurrent administration of pexidartinib decreased the $AUC_{0-\infty}$ of the CYP3A4 substrate midazolam by 57%. As the hormonal contraceptive ethinyl estradiol is a CYP3A4 substrate, there is a potential that exposure of ethinyl estradiol may decrease on concurrent administration with pexidartinib. As pexidartinib may cause embryo-fetal harm when administered to a pregnant woman, females of reproductive potential should be advised to use an effective, non-hormonal method of contraception during treatment with pexidartinib and for one month after the last dose. Males with female partners of reproductive potential should be advised to use an effective method of contraception during

treatment with pexidartinib and for one month after the last dose. Female partners of male patients should concurrently use effective contraceptive methods (hormonal or non-hormonal).

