Pexidartinib, at the assigned dose, will be offered to each patient as long as both the patient and investigator agree that it continues to be well tolerated, and there has been no evidence of disease progression. Study visits will occur at 12-week (± 7 days) intervals (i.e., every 3 cycles) for assessment of safety (AEs, concomitant meds, physical exam with weight and vital signs, hematology, and chemistry), compliance, and 24-week intervals (i.e., every 6 cycles, or as clinically indicated) for radiographic assessment of tumor response or progression. For patients without ongoing Grade 2 or greater related adverse events, frequency of on-site visits may be extended to every 24 weeks, with remote serum chemistry and hematology as well as a telephone check-in for AEs and con meds and to review remote safety laboratory data performed 12 weeks after each on-site visit; Weight, PE, Vitals, WOMAC, NRS, and IP compliance will not be performed remotely). For PVNS patients, the Sponsor will receive radiologic images for possible retrospective analysis of treatment response, to be performed by a central vendor.

At every on-site visit the six (6) completed NRS for PVNS Symptoms questionnaires will be collected and the patient will be given another one of the questionnaires to complete predose. Then the patient will be given the WOMAC questionnaire to complete predose. Once all other procedures have been completed at the visit, six (6) NRS for PVNS Symptoms questionnaires will be given to the patient with instructions and reminders to complete the daily questionnaire on an outpatient basis for the 6 consecutive days (Day -6 to Day -1) prior to the next scheduled study visit 12 weeks later and to bring the completed questionnaires back at that visit.

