14.7 Dose Modification (Extension Cohorts)

Reduction/interruption of dosing for adverse events may take place at any time during the study according to guidelines in [Table 3](#). Dose reductions should occur in increments of 200 mg/day, depending on the toxicity grade, as noted in [Table 3](#). Dose reduction/interruption guidelines for hematologic and nonhematologic treatment-related TEAEs are based on severity. Dose interruptions can be implemented at the discretion of the treating Investigator to manage intolerable or clinically significant toxicity. If a dose interruption is required, study assessments should be performed as scheduled, irrespective of the study drug delay, with the exception of PK assessments, which should be deferred until treatment is resumed. Interruptions due to toxicity

lasting >3 weeks require treatment discontinuation unless the medical monitor approves continuation.

Table 3: Dose Modifications

Event	Severity	Pexidartinib Dosage Modifications
Hepatotoxicity		
Increased ALT and/or AST	>3 to 5 × ULN	Withhold and monitor liver tests weekly. If AST and ALT ≤3 × ULN within 4 weeks, resume at reduced dose. If AST or ALT not ≤3 × ULN in 4 weeks, permanently discontinue pexidartinib.
	>5 to 10 × ULN	Withhold and monitor liver tests twice weekly. If AST and ALT ≤3 × ULN within 4 weeks, resume at reduced dose. If AST or ALT not ≤3 × ULN in 4 weeks, permanently discontinue pexidartinib.
	>10 × ULN	Permanently discontinue pexidartinib. Monitor liver tests twice weekly until AST or ALT ≤5 × ULN, then weekly until ≤3 × ULN.
Increased ALP ^a and GGT	ALP >2 × ULN with reflex test of GGT >2 × ULN	Permanently discontinue pexidartinib. Monitor liver tests including GGT twice weekly until ALP ≤5 times ULN, then weekly until ≤2 × ULN.
Increased bilirubin	TB >ULN to <2 × ULN or DB >ULN and <1.5 × ULN	Withhold and monitor liver tests twice weekly. If an alternate cause for increased bilirubin is confirmed and bilirubin <ULN within 4 weeks, resume at reduced dose. If bilirubin not <ULN in 4 weeks, permanently discontinue pexidartinib.
	TB ≥2 × ULN or DB >1.5 × ULN	Permanently discontinue pexidartinib. Monitor liver tests twice weekly until bilirubin ≤ULN.
Adverse Reactions or Other Laboratory Abnormalities		
Any	Severe or intolerable	Withhold until improvement or resolution. Resume at a reduced dose upon improvement or resolution.

ALT = alanine aminotransferase; ALP = alkaline phosphatase; AST = aspartate aminotransferase;

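### Section 12.1 explains its caution on CYP3A4 substrates only by an unknown rise in exposure, while Section 12.2 reports induction, and nothing asks sites to watch those drugs for loss of effect

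*Combined protocol and SAP*

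**What the plan says.** Section 12.1 covers interactions in both directions. For the effect of pexidartinib on other drugs, it says that "caution is warranted when administering pexidartinib to subjects taking drugs that are highly dependent on CYP3A4 for metabolism" and limits this to drugs with a narrow therapeutic index. It introduces the advice by noting that pexidartinib seems not to inhibit CYP enzymes to an important extent, and explains it with "It is not known whether systemic exposure to these medications will demonstrate an increase while patients are receiving pexidartinib". The rest of 12.1, including Table 2, concerns the effect of other drugs on pexidartinib.

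Section 12.2, headed Hormonal Contraceptives, says "Pexidartinib has been indicated to be a moderate CYP3A4 inducer" and supports this with a 57% fall in midazolam AUC from zero to infinity. The consequence it draws is for one drug: "there is a potential that exposure of ethinyl estradiol may decrease on concurrent administration with pexidartinib". The action is a non-hormonal method of contraception, which inclusion criterion 4 in Section 10.1 also requires of women of child-bearing potential.

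Two other places bear on the point. Section 12.0 sets the general rule: "Concomitant treatment is permitted if the medication is not expected to interfere with the evaluation of safety or efficacy of the study drug". Section 6.3 closes its in vitro summary with "Clinically relevant drug-drug interactions are not anticipated based upon experimental evidence of negligible CYP inhibition or induction in vitro".

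**The concern.** Sections 12.1 and 12.2 are both current instructions to sites, and they point in different directions. An investigator with a patient on a CYP3A4 substrate other than a contraceptive would turn to 12.1. The only direction named there is an increase, which suggests watching for excess effect. The one result the protocol reports is a decrease, which suggests watching for loss of effect.

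What is at stake is patient safety. For a drug with a narrow therapeutic index, a fall in exposure can mean that it stops working adequately. Such patients can be enrolled: the exclusion criteria in Section 10.2 do not mention these drugs, the rule in 12.0 is about protecting the evaluation of pexidartinib, and 12.1 itself presupposes that some patients take them.

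**Working it through.** The 57% is a reported result with no underlying data in the documents, so it cannot be reproduced. The check is a comparison of texts with one line of arithmetic.

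**Step 1: direction and size.** Input: the midazolam AUC decrease of 57% from Section 12.2.

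- Remaining exposure = 1 − 0.57 = 0.43, or 43% of the AUC without pexidartinib.

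This is a fall, opposite to the only direction that 12.1 mentions. It applies to midazolam. The documents give no figure for any other substrate.

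**Step 2: the two subsections side by side.**

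| | Section 12.1 | Section 12.2 |
|---|---|---|
| Drugs covered | CYP3A4-dependent drugs with a narrow therapeutic index | Ethinyl estradiol, with midazolam as evidence |
| Direction stated | Increase, described as unknown | Decrease, reported |
| Size | None | Midazolam AUC down 57% |
| Action | Caution, no direction and nothing to monitor | Non-hormonal contraception |

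The wider group of drugs has the outdated explanation. The current evidence is attached to a single class, and the action there is to avoid the drug, so it supplies no monitoring advice that could carry over. Neither subsection refers to the other.

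**Step 3: does anything else fill the gap?** These are the places where a monitoring instruction might be found.

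- Section 12.0 asks whether a co-medication disturbs the evaluation of pexidartinib, not whether it still works.
- Section 14.6.2 allows, after Cycle 40, a "telephone check-in for AEs and con meds" in place of an on-site visit for patients without ongoing related events of Grade 2 or above. Co-medication is recorded, but no one is told what to look for.
- Section 14.7, Table 4, asks for a medication history as part of a liver work-up.
- Section 14.7 also says that during a dose interruption "study assessments should be performed as scheduled, irrespective of the study drug delay", PK sampling excepted. It does not mention co-medication.
- Section 24.3 looks at whether co-medication alters the PK of pexidartinib, not the reverse.
- Attachment 5 lists CYP3A4 inhibitors and inducers. It has no list of substrates.
- Section 26.1 counts a clinically significant worsening of an existing condition as an adverse event. It also has sites record a clinically significant laboratory abnormality that leads to a change in other therapy. Section 26.2 has sites ask an open question about how the patient has felt.

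The Section 26 rules are the only ones that could bring a loss of effect to light, and they do so after the event.

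**The case against.** The strongest reply is that the operative instruction is already right. Section 12.1 tells sites to be careful with exactly the drugs that matter and does not say in which direction. Its explanatory sentence is incomplete, but it does not say that exposure cannot fall. A physician who reads on to 12.2 finds the mechanism stated in general terms, with an effect size. The clearest consequence, failure of hormonal contraception with a drug that may harm a fetus, is dealt with in 12.2 and in eligibility. The adverse-event rules give a general safety net. All of this stands, and it keeps the point minor. It does not remove the point, because no text connects the induction result to the caution or says what to monitor.

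A reader might infer three stronger things that the documents do not support.

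- **That sites are told something false, or that the protocol gives no protection.** The caution is sound; one explanatory sentence is outdated and one instruction is missing. The Investigator's Brochure, to which Section 26.0 refers sites for safety information, may already cover substrate monitoring. It was not seen.
- **That Section 6.3 is a second operative contradiction.** It is nonclinical background, ties its conclusion to in vitro evidence, and opens by sending readers to the Brochure for updated information.
- **That a co-medication would rebound by a calculable amount when pexidartinib is held.** One could invert 0.43 to get a fold-rise, but this requires that a patient takes such a drug, that its dose was raised on treatment, and that induction wanes within the hold. The documents give no time course for induction and no data on the other two conditions, so no figure is offered.

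**Conclusion.** The point holds as an inconsistency in safety guidance. The explanation in 12.1 names only an unknown increase, 12.2 reports a decrease, and no instruction asks sites to watch CYP3A4 substrates other than contraceptives for loss of effect.

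The only size available is the 43% of exposure remaining for midazolam. Applying the direction, though not the size, to other substrates rests on the protocol's own description of pexidartinib as a CYP3A4 inducer and on its own extension of that finding to ethinyl estradiol. The number of patients on affected drugs is not known and none is assumed. The conclusion covers the protocol text and not the Brochure. No endpoint, power or error rate is touched. The correction is minor but worth making, because it uses information that the protocol already holds.

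**What to change.** In Section 12.1, replace the sentence about an unknown increase with wording such as:

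> Available data indicate that pexidartinib is a moderate inducer of CYP3A4; exposure to CYP3A4 substrates may decrease (midazolam AUC fell 57%, see Section 12.2; the size for other substrates is not known). Monitor narrow-therapeutic-index CYP3A4 substrates for loss of effect, and review their dosing if pexidartinib is interrupted or stopped.

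The last clause asks for a review and prescribes no adjustment, since the time course is not given. It has a practical occasion: Table 3 requires pexidartinib to be withheld when ALT or AST exceeds 3 × ULN, with up to 4 weeks for recovery.

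Updating the in vitro conclusion in Section 6.3 to mention the midazolam result is optional tidying.

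The cost is one text edit in the next amendment, with no new scheduled visit or study sample. The downside is an occasional extra check on a co-medication, which for some drugs may mean a local test. It is most likely to need an unscheduled contact after Cycle 40, when visits are 12 weeks apart and on-site visits may be 24 weeks apart.
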